### 9.3 POPULATIONS FOR ANALYSES

The primary analyses will be conducted including those participants who have used Gentamicin flushes for at least half of the days during their 6-month intervention period if data is available for the number of UTIs that they experience during the period when they are using these flushes. Additional analyses will be conducted using an intent-to-treat orientation, using all participant data that is available.

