#### **6.5.1 RESCUE MEDICINE**

Participants experiencing a symptomatic UTI may be prescribed an oral antibiotic by their treating physician. The name and dose (if available) will be documented in the study record. It is up to the participant and/or their caregiver to seek treatment for an active UTI. The study will not provide any medications other than the study products.

Likewise, it is possible that participants might be prescribed an antibiotic for another reason (i.e. not for a UTI). Regardless of the reason, participants will be instructed to pause their daily instillations while undergoing treatment with an antibiotic for any reason. They are then to resume their study treatment upon finishing their outside antibiotic. The participants will document this in their dosing diaries and the information will be maintained in the subject's research records. This issue will also be discussed during the bi-weekly phone calls.

Participants may use non-pharmacologic strategies to help manage their urinary health, such as cranberry juice. The use of these types of treatments will be documented at the study visits, and during the bi-weekly phone calls.

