## 7 STUDY INTERVENTION DISCONTINUATION AND PARTICIPANT DISCONTINUATION/WITHDRAWAL

### 7.1 DISCONTINUATION OF STUDY INTERVENTION

Participants may elect to discontinue the study intervention for any number of reasons (not inclusive list): burden of study procedures, side effects, caregiver limitations, etc. They will be educated on signs and symptoms of toxicity (see Section 8.2) and instructed to notify the study team and their physician for advice on discontinuation of study treatment. If a participant develops COVID-19 while participating in this study, the study team will make every effort to keep the participant in the trial. Participants with COVID-19 will remain in the study unless, for medical reasons, they can no longer participate.

Participants will be asked about the reasons for withdrawal from the study when self-initiated.

Regardless of the reason, discontinuation of the study treatment does not mean withdrawal from the study since the study uses an intent –to-treat design. If a participant decides to stop using the study product, and they are willing, they will remain enrolled in the study. This means that study procedures, including bi-weekly phone calls and study visits will go on as scheduled. No drug taper is required when subjects discontinue the study treatment – they may stop immediately. These subjects will also complete the study's final assessments, if willing.

Regarding the discontinuation of treatment, the following information will be documented in the study record:

- Reason for discontinuation of intervention (i.e. treatment).
- Date of last dose.
- Willingness to continue in the study.

If a participant decides to discontinue the study intervention in light of a new or exacerbated clinical finding, we will report the finding on the Adverse Event case report form, and report to the necessary entities as outlined in the Events Reporting Schedule.

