### 9.4.2 ANALYSIS OF THE PRIMARY EFFICACY ENDPOINT(S)

To test for significant differences in the incidence of UTIs across periods, as mentioned above, paired samples t-tests will be conducted using log-transformed infection rates rather than the raw rates. We may then subsequently re-analyze this data using a Generalized Linear Mixed Model (GLMM) with log link and a Poisson distribution, as is appropriate for count outcomes data.

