**Statistical Analysis Plan**

**6/23/2023**

### **Statistical Analysis Plan**

All data were examined for completeness and outliers before hypothesis testing. Categorical data was summarized in terms of frequencies, presented as n (%), and continuous data will be summarized in terms of means (standard deviations). Participant demographics and clinical status were evaluated using descriptive statistics. All efforts were made to recruit a balanced sample representative of persons with SCI/D. Statistical significance was set at  $p < 0.05$  for group comparisons with a 95% confidence interval.

To test for significant differences in the incidence of UTIs across periods (six months pre-treatment, six-month treatment, one-month post-treatment, six months post-treatment) an incidence rate per person month was determined by comparing the total number of UTIs in relation to duration, reflecting all participants across six months. The incidence rate ratio was determined by comparing the different timepoint ratios in relation to pre-treatment ratio. Confidence intervals and p values were calculated for rates and rate ratios. This approach analytical was used to satisfy small sample size calculations, as appropriate with count outcomes data (Hypothesis 1). To assess the impact of the study intervention on our Secondary Endpoint, bladder, and bowel complications (Hypothesis 2), and Tertiary Endpoints, QOL (Hypothesis 3), paired t tests were used to test differences in scores across survey measures.

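### The protocol's primary analysis set is selected on adherence after treatment starts, with intent-to-treat only additional; this sits badly with section 7.1 and the SAP

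*Protocol*

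**What the plan says.** Protocol section 9.3 defines the primary set as "including those participants who have used Gentamicin flushes for at least half of the days during their 6-month intervention period", subject to the condition "if data is available for the number of UTIs that they experience during the period when they are using these flushes". It then commits to a second analysis: "Additional analyses will be conducted using an intent-to-treat orientation, using all participant data that is available".

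Protocol section 7.1 says that stopping study treatment is not withdrawal "since the study uses an intent –to-treat design". Calls and visits go on as scheduled for those who are willing.

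The SAP, dated after the protocol, does not repeat the half-of-days rule and names no analysis set. It computes UTIs per person-month "reflecting all participants across six months", then rate ratios against the pre-treatment period. It does not say whether duration means calendar time or time on flushes.

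Section 3 (endpoint), section 4.1 and section 9.1 use the whole six-month treatment period. Section 6.1.1 starts that period at the first instillation, and section 4.1 fixes six months at 180 days. Section 6.5.1 adds that "participants will be instructed to pause their daily instillations while undergoing treatment with an antibiotic for any reason".

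Section 9.2 gives N = 15 for at least 80% power and ties that number to participants who complete the study.

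**The concern.** Whether a participant reaches half of the days is known only after treatment has started, and participants know that they are on active drug. Someone who stops because UTIs keep coming would leave the primary set, and the remaining set would look better than the treated group. The protocol also takes the trouble to follow stoppers, then leaves those below half of the days out of its main result.

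A lesser matter is the counting window. The data-availability condition in 9.3 speaks of UTIs while flushes are in use, and the endpoint speaks of six months. Flushes stop during antibiotic courses, so the two windows differ even for adherent participants. Neither section 9.3 nor section 9.4.2 gives a denominator for the rate.

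**Working it through.** **1. The plan's own figure.** Section 9.2 assumes a 50% reduction (log ratio ln 2 = 0.693) and a paired t-test on log rates. It gives no SD and no sidedness, so N = 15 cannot be reproduced outright. Solving backwards with two-sided alpha 0.05, 80% power and N = 15 gives a standardised difference of 0.778. The SD is then 0.693/0.778 = 0.89, and the standard error is 0.89/√15 = 0.230. This SD is not in the documents.

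**2. Effect of the half-of-days rule with no drug effect.** Assumptions:
- Individual UTI rates are gamma (shape 2) with population mean 2 or 3 per 180 days. Counts are Poisson, with the same rate before and after.
- Entry needs at least 2 prior UTIs (section 5.1).
- 25% or 50% stop at their second on-treatment UTI. Those who stop before day 90 are excluded.
- The ratio is mean count after divided by mean count before.

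| Mean | Stopping | Excluded | Ratio, all | Ratio, retained | Retained/all | Retained/all, log rates |
|---|---|---|---|---|---|---|
| 2 | 25% | 9.3% | 0.785 | 0.744 | 0.947 | 0.948 |
| 2 | 50% | 18.8% | 0.787 | 0.690 | 0.876 | 0.887 |
| 3 | 25% | 12.7% | 0.876 | 0.838 | 0.957 | 0.949 |
| 3 | 50% | 25.2% | 0.877 | 0.784 | 0.895 | 0.883 |

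The retained ratio is thus a further 4-12% lower on mean counts and 5-12% lower on log rates. The smallest and largest shifts are -ln 0.957 = 0.044 and -ln 0.876 = 0.132. Divided by 0.230, these are about 0.2 to 0.6 standard errors at N = 15.

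The all-participant ratios are already below 1. That is regression to the mean from the entry rule. It affects both sets and is a separate matter.

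**3. The same model with the planned 50% reduction.** Fewer participants reach a second UTI, so 4-12% are excluded. The further difference is about 5-11% on mean counts and 3-8% on log rates.

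**4. Stopping unrelated to UTIs.** With stopping on a random day, retained/all is 1.00 on 180-day rates, on-flush rates and log rates.

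**5. Antibiotic pauses.** Two courses of 7 days to three of 14 days (an assumption) take 14 to 42 of 180 days, or 8-23%, out of an on-flush window. To fall below half of the days through pauses alone takes 90/14 = 6.4, so 7 courses, or 90/7 = 12.9, so 13 courses. Pauses by themselves exclude essentially nobody.

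**6. Why the window needs stating.** Take 2 UTIs in the prior 180 days, flushes on 90 of 180 days, 1 UTI on flushes and 1 off.
- All UTIs over 180 days: 2/2 = 1.0.
- On-flush UTIs over on-flush days: (1/90 × 180)/2 = 1.0.
- On-flush UTIs over 180 days: 1/2 = 0.5.

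One participant can move from no change to the whole planned effect.

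**7. Power if all treated participants are primary.** Let a share f get no benefit, so the mean log reduction is 0.693 × (1 − f), with SD 0.89. The lower power in each pair adds the mixture variance f(1 − f) × 0.693². Those with no benefit are added to 15 completers.
- f = 10%: 15/0.9 gives 17 analysed and power 75-77%.
- f = 20%: 15/0.8 gives 19 analysed and power 69-73%.

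**The case against.** **The rule is explicit, and intent-to-treat is planned.** This stands. A reader might infer that the intent-to-treat analysis was dropped, but section 9.3 commits to it. Section 9.4.3 also allows sensitivity analysis for participants who stop treatment. The issue is which analysis is primary.

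**Section 7.1 does not say which analysis is primary, and a single-arm study has no randomised comparison to protect.** Both points are true. Section 7.1 uses the term to explain why stoppers stay in follow-up. The objective in section 3 speaks of incidence during treatment, so an adherent set can be defended as answering a real question. What remains is a design label that does not match the primary set, and possible selection on outcome.

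**The SAP may govern.** It is later and refers to all participants. A reader might infer that it flatly contradicts 9.3 or has replaced it. It names no analysis set, so it supports neither inference. The primary result rests on the adherent set only if 9.3 governs.

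**The bias is assumed.** Section 7.1's examples of reasons for stopping are burden, side effects and caregiver limits, though it says that the list is not complete. A reader might infer that the result must favour gentamicin. The documents do not show this, and random stopping gives no difference.

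**The window clause is only a condition on data.** This largely stands. A reader might infer that 9.3 redefines the endpoint as on-flush UTIs, but sections 3, 4.1, 6.1.1 and 9.1 point to the full period.

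**The power loss in step 7 is a harsh case.** Someone below half of the days may have up to 89 days of exposure, so no benefit at all is pessimistic.

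**Conclusion.** The point holds as a matter of ordering and consistency. Section 9.3 makes a set chosen on post-baseline adherence primary, and this sits badly with section 7.1 and with the later SAP. The possible tilt towards gentamicin is modest and needs both conditions: that 9.3 governs, and that some stopping is driven by UTIs. It is then the 4-12% of step 2 with no drug effect, or the smaller log-rate shift of step 3 under the planned reduction. The stopping pattern and the rate distribution are assumptions. The unclear window and the missing denominator are lesser points that need wording. The difference between the protocol's paired t-test and the SAP's rate ratios is a separate issue, and the point does not depend on it. It should be fixed, because the remedy is cheap.

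**What to change.** - **Primary set:** every participant with at least one instillation, including treated participants later withdrawn or replaced under section 7.2, with the data available.
- **Counting:** all UTIs on days 1-180 from first instillation, whether or not instillations continued, with days observed as the denominator. Apply this to whichever primary method is kept.
- **Supportive set:** keep the half-of-days set, and state its counting window and how antibiotic pauses count towards the half.
- **Alignment:** use the same wording in section 7.1, section 9.3 and the SAP.
- **Section 9.2:** it already ties N = 15 to completers. Add only that power for the all-treated set may be lower, illustratively 69-77% on the assumptions of step 7.

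**Cost:** no new data collection. Calls already continue for willing stoppers (section 7.1), and medical records may fill gaps (section 7.3), though some participants will have fewer than 180 days observed. The estimate may be smaller and the stated power somewhat lower. The question about adherent users moves to a supportive analysis. Regression to the mean from the entry rule is not removed.

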## 9.4 STATISTICAL ANALYSES

### 9.4.1 GENERAL APPROACH

All data will be examined for completeness and outliers before hypothesis testing. Categorical data will be summarized in terms of frequencies, presented as n (%), and continuous data will be summarized in terms of means (standard deviations). Participant demographics and clinical status will be evaluated using descriptive statistics. These analyses will be conducted after all data has been collected. All efforts will be made to recruit a balanced sample representative of persons with SCI/D. Missing data will be handled using common statistical methods such as multiple imputation and the estimation maximization approach.

All statistical procedures will be run using either SPSS or the statistical package R. Statistical significance will be set at  $p < 0.05$  for group comparisons and all models.

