- We anticipate the ability to screen at least 30-50 participants in order to obtain a sample of 25 potential participants following eligibility screening with the goal of enrolling and retaining a minimum of 15 participants..
- Special efforts will be made to recruit minority participants by ensuring that all potential eligible minority participants are contacted and invited to participate.

---

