### **Second Visit**

- Phone calls in the month preceding the projected follow-up window.
- Can use email if preferred by participant.
- Send letter asking for participant to call or email the study team if no contact is made.
  - Provide alternatives to facilitate completing outcome assessments: surveys over phone, urine analysis done at a clinic closer to home, etc.

Since some of the information to be collected for this follow-up may be available in participants' medical records, e.g., documentation of treatment for a UTI, study staff will review records before contacting subjects and query subjects if discrepancies are observed. If the follow-up cannot be completed with the subject, data from their medical record may be entered into the study database. All encounters will be documented in the study record. Individuals who are deemed "unreachable" will be withdrawn from the study and categorized as "Lost-to-follow up."

Participants will be asked if they would like to participate in a brief survey about their experience in the trial. When possible, these questions will be asked at the end of their follow up. For those who already completed their third follow up, the study team will contact them via phone or e-mail asking the same questions. Three to four contact attempts will be made to participants to gauge their interest in completing this post-intervention survey. Email may be used if preferred by participant. If a participant cannot be reached after these attempts they will be considered uninterested in the survey. All participants will be thanked for their participation in the study either verbally or by letter.

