### 9.4.3 ANALYSIS OF THE SECONDARY AND TERTIARY ENDPOINT(S)

To assess the impact of the study intervention on our Secondary Endpoint, bladder, and bowel complications (Hypothesis 2), and Tertiary Endpoints, QOL (Hypothesis 3), and Participation (Hypothesis 4), a similar analytic approach will be used as was used for Hypothesis 1. The outcomes for these hypotheses are all continuous and therefore paired t tests or GLMM will be used. Our plan for handling missing data across all study analyses will include the use of common statistical methods to handle missing data such as multiple imputation and the estimation maximization approach. As appropriate, we may employ sensitivity analysis to assess the effect of data that is not missing at random such as when participants stop using the research treatment but continue to be willing to participate in the study's assessments.

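### The plan lets the EM approach fill in missing scores before a paired t-test; used that way, the false-positive rate would be about 7-14% at 12-25% missing, not 5%

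*Protocol*

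**What the plan says.** Protocol 9.4.1 sets the general rule: "Missing data will be handled using common statistical methods such as multiple imputation and the estimation maximization approach". Section 9.4.3 widens its scope: "Our plan for handling missing data across all study analyses will include the use of common statistical methods to handle missing data", and gives the same two examples. It also allows a sensitivity analysis for data that are not missing at random.

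For the secondary and tertiary scores, 9.4.3 says: "The outcomes for these hypotheses are all continuous and therefore paired t tests or GLMM will be used". The SAP keeps only the first option, for Hypotheses 2 and 3: "paired t tests were used to test differences in scores across survey measures". It does not mention missing data. Significance is set at 0.05 in both documents; sidedness is not stated.

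Scores are collected twice, at baseline and at about six months (8.1). Section 3 lists eight score endpoints, two secondary and six tertiary. No dropout rate is given. The nearest figure is in 5.5, which aims for a "sample of 25 potential participants following eligibility screening with the goal of enrolling and retaining a minimum of 15 participants".

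**The concern.** EM can be used in two ways. It can give maximum-likelihood estimates of the means and covariances, from which a correct standard error can be derived. Or, as an option in a statistics package, it can return one completed data set in which each missing value is replaced by its prediction. A paired t-test cannot use the first output directly, but it will accept the second. An analyst who takes EM from the protocol and the paired t-test from the SAP is therefore led to the single completed data set.

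That combination fails for two reasons. The filled-in scores lie exactly on the regression line, so the differences vary too little. The test also divides by the full number of participants, although only those with both scores carry information on change. Both make the standard error too small, so p-values are too low and confidence intervals too narrow. With eight score endpoints in a single-arm, unblinded study, and the choice of method left open, a nominally significant improvement in a score could come from the fill-in alone.

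**Working it through.** **The plan's own figures.** The plan states no error rate or dropout rate for the scores, so there is nothing to reproduce on this point. Its one sample-size figure (9.2: 15 completers for at least 80% power) concerns log UTI rates and cannot be checked, because the SD of the log change is not given.

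**Inputs.**
- From the documents: significance level 0.05 (9.4.1); two score occasions (8.1); paired t-test (SAP); 15 completers (9.2); 25 potential participants (5.5).
- Assumed: two-sided testing; pre-post correlation r from 0.3 to 0.9; bivariate normal scores with equal variances; no true change; baseline complete and six-month scores missing completely at random.

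**Method.** Let N be the number of participants, m the number of missing six-month scores and k = N - m. With baseline complete, the EM solution is the completers' regression of six-month score y on baseline x. Each missing y is replaced by a + b·x. The test is then t = mean(d) / (SD(d)/√N) with d = y - x, referred to N - 1 degrees of freedom.

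**Hand check, N = 25, m = 10, r = 0.5, unit variances** (large-sample approximation):
1. True variance of the mean change: (1 - r²)/k + (1 - r)²/N = 0.75/15 + 0.25/25 = 0.060, so SE = 0.245.
2. Variance of d among completers: 2(1 - r) = 1.00. Among filled-in cases: (1 - r)² = 0.25. Pooled: (15 × 1.00 + 10 × 0.25)/25 = 0.70.
3. Variance the t-test reports: 0.70/25 = 0.028, so SE = 0.167.
4. Ratio: 0.167/0.245 = 0.68.
5. The critical value for 24 degrees of freedom, 2.064, acts like 2.064 × 0.68 = 1.41. The two-sided tail beyond 1.41 is 18.2% on k - 2 = 13 degrees of freedom.

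The simulation gives 18.5% for this case.

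**Simulation** (40,000 trials per cell, missing completely at random):

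| Missing / N | % missing | EM fill-in + paired t-test, r = 0.3 to 0.9 | Complete-case paired t-test |
|---|---|---|---|
| 2/17 | 11.8 | 7.2-8.2% | 4.7-5.1% |
| 2/15 | 13.3 | 7.6-8.6% | 4.8-5.2% |
| 3/18 | 16.7 | 8.5-10.1% | 4.9-5.0% |
| 3/15 | 20.0 | 9.6-11.3% | 5.0-5.2% |
| 4/19 | 21.1 | 9.6-11.9% | 5.0-5.1% |
| 5/20 | 25.0 | 10.8-13.6% | 4.8-5.0% |
| 10/25 | 40.0 | 16.7-22.9% (16.7-20.8% for r = 0.3 to 0.7) | 4.8-5.1% |

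**Variations at 10 of 25 missing.**
- Missingness dependent on baseline raises the fill-in rate to 20.5-27.4% (r = 0.3 to 0.9).
- One random residual added to each prediction, still a single data set, lowers it only to 13.7-17.4%.
- Multiple imputation (20 imputations, Rubin's rules, small-sample degrees of freedom; 20,000 trials) gives 3.3-3.7%.
- EM/maximum-likelihood estimates with a correct standard error give 4.2-4.4%.

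The fault is therefore the single fill-in followed by an ordinary t-test, not EM as an estimation method.

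**The case against.** The strongest reply is that the documents do not commit to this procedure. Multiple imputation is named first, both methods are only examples, 9.4.3 permits a GLMM that needs no filled-in data, and a paired t-test can simply drop incomplete pairs. The SAP, written largely in the past tense, reports paired t-tests and no imputation, so complete-case analysis is a natural reading, and that stays at about 5%. All of this stands. It makes the problem conditional, but does not remove it: EM is named for all analyses, and no text excludes the fill-in.

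Three stronger readings are tempting, and the documents support none of them.

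- **That 40% attrition is planned.** A reader might infer this from 25 falling to 15 in 5.5. That passage mixes non-enrolment with later loss, and 15 is a minimum. Ten of 25 scores missing requires that all 25 give a baseline score and that all ten losses follow it. Section 7.1 keeps willing participants in assessments after they stop treatment, and 7.3 offers surveys by phone. Section 7.2 provides for replacement. Replacement adds completers, but it does not supply the lost score in the additional intent-to-treat analyses of 9.3.
- **That the primary endpoint is inflated too.** The simulations concern continuous scores only. Section 9.3 limits the primary analysis to participants with UTI data, 10.1.9.1 makes the medical record the source for UTI counts, and 7.3 says that, where follow-up fails, "data from their medical record may be entered into the study database".
- **That EM must go altogether.** With a correct standard error it holds its level, as shown above.

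**Conclusion.** The point holds as a conditional defect that should be corrected. The protocol names a method which, joined to the SAP's test in the most direct way, gives invalid p-values for the scores. If it were used that way, the false-positive rate would be about 7-14% at 12-25% missing, and about 17-21% in the upper-end case of 10 of 25 (r = 0.3 to 0.7), against a nominal 5%.

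These figures rest on the assumed correlation, normality, two-sided testing and scores missing completely at random. Missingness related to baseline would make them worse. How many scores will be missing, and whether EM fill-in will be used, cannot be determined from the documents. The demonstrated reach is the secondary and tertiary scores.

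**What to change.** In protocol 9.4.1 and 9.4.3 and in the SAP, state that missing scores will not be replaced by a single EM-completed data set, and name one method for the score endpoints:

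- a likelihood-based mixed model fitted to all observed scores; or
- multiple imputation with Rubin's rules and small-sample degrees of freedom, with the number of imputations stated (20 were used in the check above).

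Report the complete-case paired t-test beside it as a check, with the number of participants contributing both scores. If EM is kept as an estimation method, say how its standard error will be obtained.

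The cost is a few sentences in each document. No new data or participants are needed. Confidence intervals will be somewhat wider than after a fill-in, which reflects the information actually available.
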